CD	Cushing's disease
CI	Confidence Interval
CMH	Cochran–Mantel–Haenszel
CNS	Central Nervous System
eCRF	Electronic Case Report/Record Form
CRO	Contract Research Organization
CS	Cushing's syndrome
CSR	Clinical study report
C-SSRS	Columbia Suicide Severity Reporting Scale
CT	Computerized Tomography
CTCAE	Common Terminology Criteria for Adverse Events
DBP	Diastolic Blood Pressure
DHEA(S)	Dehydroepiandrosterone (Sulfate)
DMC	Data Monitoring Committee
DS&E	Drug Safety and Epidemiology
DXA	Dual-energy X-ray absorptiometry
ECG	Electrocardiogram
EDC	Electronic Data Capture
FAS	Full Analysis Set
FSH	Follicle-stimulating hormone
GFR	Glomerular Filtration Rate
eGFR	Estimated Glomerular Filtration Rate
ICH	International Conference on Harmonization
IE	Independent Endocrinologist
IEC	Independent Ethics Committee
IRB	Institutional Review Board
IRT	Interactive Response Technology that includes Interactive Voice Response System and Interactive Web Response System
ITT	intent-to-treat
KOL	key opinion leaders
LAR	Long Acting Release
LC-MS/MS	Liquid chromatography-tandem mass spectrometry
LFT	Liver Function Test
LH	Luteinizing Hormone
LLN	Lower Limit of Normal
MoA	Mechanism of Action
MRI	Magnetic Resonance Imaging
mUFC	mean Urine Free Cortisol

PAS	Pharmacokinetic Analysis Set
PD	Pharmacodynamic
PK	Pharmacokinetic
PPS	Per-Protocol Set
PRO	Patient-Reported Outcomes
PT	Preferred Term
QoL	Quality of Life Questionnaire
QTc(F)	QT corrected (Fridericia QT formula)
eSAE	Electronic Serious Adverse Event
SAS	Safety Analysis Set
SBP	Systolic Blood Pressure
s.c.	Subcutaneous
SC	Steering Committee
SD	Standard Deviation
SEC	Safety Event Categories
SMR	standardized mortality ratio
SOP	Standard Operating Procedure
SS	Safety Set
TBIL	Total bilirubin
TdP	Torsades des Pointes
UFC	Urine Free Cortisol
ULN	Upper Limit of Normal

Glossary of terms

Assessment	A procedure used to generate data required by the study
Biologic Samples	A biological specimen including, for example, blood (plasma, serum), saliva, tissue, urine, stool, etc. taken from a study subject or study patient
Baseline value	Value from the last assessment prior to first dosing
Complete Response	Defined as mUFC \leq ULN
Core phase	Includes both Period 1 and Period 2; Visits Day 1 through Week 48.
Enrollment	Point/time of patient entry into the study when informed consent must be obtained (i.e. prior to starting any of the procedures described in the protocol)

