2.2.6 ECG Monitoring

Cardiac monitoring will include 12-lead Safety ECGs at pre-dose (Day 1) and 1.5 hours post-dose at each visit the patient receives study drug. The Safety ECGs are the primary cardiac safety assessment, and their rationale is to assess the maximum change in QTcF in each individual patient each time they receive study drug at the site. The 12-lead safety ECGs are read in real-time on-site by the PI or other qualified physician (e.g., cardiologist), and if there is QT prolongation (QTcF > 480 ms or increase > 60 ms from baseline assessment), patients are to be managed according to the QT Monitoring Flow Chart in [Figure 7-2](#).

In addition, 24-hour continuous 12-lead Holter recordings will be performed at baseline, Weeks 2, 12, 14, 36, and as applicable at Week 72 and at the end of treatment visit in the optional Extension phase. The 24 hour Holter assessments are not intended to provide real-time assessment of cardiac intervals and cardiac rhythm; the recordings are read centrally.

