7.1.1.3 Patient demographics and other baseline characteristics

The following patient demographics and baseline characteristics will be collected on the eCRF:

- Demography including date of birth, sex, predominant race and ethnicity (where permitted).
- Height, weight and waist circumference (see [Section 7.2.2.3](#)).
- Medical history (e.g., important medical, surgical, and allergic conditions from the patient's medical history which could have an impact on the patient's evaluation) / current medical conditions (e.g., all relevant current medical conditions which are present at the time of signing informed consent). Ongoing medical conditions, symptoms and diseases which are recorded on the Medical History eCRF should include the toxicity grade when applicable.
- Information on the most recent prior medical therapy for CD will be collected and will include information on drug, dose, duration of therapy and outcomes provided such data are available.
- Where possible, diagnoses and not symptoms will be recorded. Cushing's disease history together with the medication/treatment used will be collected.
- Prior and concomitant medications.

All assessments to be completed and documented during screening and at baseline are detailed in [Table 7-1a](#).

Day 1 assessments / samples should be taken before the patient receives study drug as these values will be considered the baseline values for the study. Where multiple values are available for a parameter prior to study drug, the last value prior to the start of study drug will be considered the baseline value.

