7.2.2.6 Cardiac assessments

Cardiac monitoring will include 12-lead Safety ECGs, which are the primary assessment of safety at study visits. The 24 hour Holter assessments are not intended to provide real-time assessment of cardiac intervals and cardiac rhythm.

Table 7-6 ECG collection plan

Week	Day	Time point	ECG Type	Central or Local reading reading
Post wash-out (up to Week -3)	up to -15	Anytime	12 Lead	Local
-2 to -1	-14 to -1	Anytime	12 Lead	Local
-2 to -1	-14 to -1		24-hour Holter	Central
1	1	Pre-dose	12 Lead	Local
1, 2, 5, 8, 12, 14, 17, 20, 23, 26, 29, 32, 36, 40, 44	1, 15, 36, 57, 85, 99, 120, 141, 162, 183, 204, 225, 253, 281, 309	1.5 hours Post-dose	12 Lead	Local
48*	337*	Anytime for patients not continuing in extension	12 Lead	Local
2, 12, 14, 36	15, 85, 99, 253	Start at Pre-dose	24-hour Holter	Central
Post Treatment Follow-up week 2, 5, 8, 12**	15, 36, 57, 85**	Anytime	12 Lead	Local
Post Treatment Follow-up week 2, 12**	15, 85**	Anytime	24-hour Holter	Central
Optional Extension: 48*, 60, 72, 84, 96 and every six month afterward ***	337*, 421, 505, 589	1.5 hours Post-dose	12 Lead	Local
End of treatment extension visit		Anytime	12 Lead	Local
Optional Extension: 72	505	Start at Pre-dose	24-hour Holter	Central
End of treatment extension visit****			24-hour Holter	Central
Post Treatment Follow-up	Last dose + 30d	Anytime	12 Lead	Local
Unscheduled assessment		Anytime	12 Lead	Local

Week	Day	Time point	ECG Type	Central or Local reading reading

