7.2.2.6.2 Electrocardiogram (ECG)

Twelve-lead safety ECGs are collected at the study sites according to [Table 7-1a](#), [Table 7-1b](#), [Table 7-2](#), and [Table 7-6](#). At each visit when a study drug dose is administered, the safety ECG should be collected at 1.5 hours post-dose (approximately at the time of C_{max}).

Twelve-lead safety ECGs are collected at the study site using ECG equipment provided by or validated by vendor. This ECG must be read on site by a qualified physician (e.g., the investigator, or another qualified physician such as a consulting cardiologist) at the time they are collected and documented on the ECG eCRF.

Each 12-lead Safety ECG tracing must be labeled with the:

- study number
- patient initials
- patient number
- date and time

and kept in the source documents at the study site. The clock on the ECG machine must be synchronized with the central clock on a daily basis.

Record the following on the eCRF:

- date and time of ECG
- heart rate
- PR interval
- QT and QTcF interval
- QRS duration

The Fridericia QT formula (QTcF) to correct for variations in heart rate must be used for clinical decisions.

The purpose of the safety ECG is to identify patients with clinically significant ECG abnormalities. On the day of the first study drug administration (Day 1), pre-dose ECGs must be done in triplicate. The mean of the QTcF from these 3 tracings is used as the baseline QTcF to be compared with subsequent ECGs.

ECGs with clinically significant abnormalities must be reported on the ECG eCRF. The overall interpretation will be collected with a Yes/No statement to confirm if any clinically significant abnormalities are present which need to be specified further.

A “notable ECG abnormality” is defined as:

- Day 1 only: an increase in QTcF > 30 msec at 1.5 hours post-dose, compared to the mean pre-dose baseline QTcF from the same day
- QTcF > 480 msec with acute cardiovascular risk, as assessed by a consulting cardiologist
- Any QTcF > 500 msec, confirmed by a consulting cardiologist
- QTcF increase > 60 msec from baseline.

Notable ECG abnormalities must be recorded on the Adverse Events eCRF page. If there is a notable abnormality, then a cardiology consult should be obtained as soon as possible, and the Novartis Medical Monitor for this trial notified of the event.

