7.2.2.7 QT monitoring

[figure not shown]
QT monitoring will occur as follows:

- On the first day of the first administration of osilodrostat (Day 1), pre-dose baseline ECGs must be done in triplicate. The mean of the QTcF values from these three ECG tracings is used to determine the mean baseline QTcF.
- On Day 1, if the safety ECG (1.5 hours post-first dose of osilodrostat) shows an increase in QTcF > 30 msec from the mean baseline value, or the QTcF is > 480 msec, then the patient must be discontinued from study. The ECG reading should be performed in triplicate (to determine a mean value) and reviewed promptly by a consulting cardiologist before discontinuing the patient from osilodrostat therapy.
- If at any following visit, a QTcF > 480 msec is observed or an increase of the QTcF of > 60 msec compared to baseline mean QTcF assessment, then two additional ECGs, each 2-3 minutes apart, need to be taken after the initial ECG. The mean QTcF from the triplicate ECGs will be determined. If the mean QTcF is > 480 msec or the mean QTcF increase is > 60 msec compared to baseline, the patient has to interrupt study drug while an urgent cardiology consultation is obtained to re-evaluate the ECG and perform a clinical consultation. If immediate treatment is required for patient safety, this should be initiated at the study site without delay and without waiting for confirmation by a cardiologist.

Based on the cardiologist consultation, the following should occur:

- If a mean QTcF > 480 msec is NOT confirmed, no further action needs to be taken.
- If the cardiologist confirms a mean QTcF > 500 msec, the patient has to discontinue according to the discontinuation procedure described in [Section 7.1.4](#). and an unscheduled PK sample is to be collected. The patient must remain under observation until the QTcF is < 480 msec and serum electrolytes, calcium, and magnesium are measured and the results normal. This observation may be done at the site, in an Emergency Room, or a cardiology clinic, as appropriate and depending upon local resources.
- If the cardiologist confirms that QTcF > 480 msec, osilodrostat treatment is temporarily interrupted and a thorough evaluation is performed to assess the patient for acute cardiovascular risk, and for possible underlying heart disease that needs additional evaluation and management. In addition, an unscheduled PK sample will be collected.

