2.1.1 General definitions

Study drug

Through out the SAP, investigational drug refers to osilodrostat, and study treatment/ study drug refers to osilodrostat or placebo.

Date of study treatment

The start date of study treatment is defined as the first date when a nonzero dose of study treatment was administered and recorded on DAR eCRF. The date of first administration of study treatment in period 1 will be referred as the start date of study treatment.

The last date of study treatment is defined as the last date when a nonzero dose of study drug was administered and recorded on DAR eCRF.

Study day

Study day is used to represent an evaluation, a measurement or an event (e.g. AE onset, laboratory abnormality occurrence, disease progression, etc). The study day is calculated as

Study day = date of assessment –start date of study treatment + 1 (if date of assessment is after start date of study treatment)

Study day = date of assessment –start date of study treatment (if date of assessment is before start date of study treatment)

For any assessment or events such as baseline characteristics or medical history that is supposed to occur prior to start date of the study treatment, study day will be negative. There is no Day 0 defined.

Study day associated with a UFC assessment

The study day associated with a UFC assessment at any particular visit is defined as the study day of the last UFC sample collection for that visit.

Time unit

A year length is defined as 365.25 days. A month length is 30.4375 days (365.25/12). If duration is reported in months, duration in days will be divided by 30.4375. If duration is reported in years, duration in days will be divided by 365.25.

Baseline

Baseline values for efficacy and safety evaluations are defined as the last assessment available before or on the start date of study treatment. If patients have no assessments as defined above, the baseline result will be missing.

Follow up

Regular safety follow-up is scheduled at 30 days after the last date of study treatment. In addition, for patients who discontinued study treatment during Period 1 (Weeks 1 to 12), reasonable efforts should be made to follow the patients and perform the assessments as indicated in protocol visit evaluation schedule table (protocol Table 7-1a) up to and including Week 12. The data collected during the follow up visits in Period 1 will be used as sensitivity analysis for efficacy, and will be used for safety.

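### Both SAPs set baseline by calendar date, so read literally the QTcF baseline is the single Day 1 post-dose ECG rather than the protocol's pre-dose triplicate mean (descriptive ECG tables only)

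*SAP*

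**What the plan says.** **SAPs.** Section 2.1.1 of the core SAP (1 April 2019) and of the final SAP (1 December 2020) carry the same sentence: "Baseline values for efficacy and safety evaluations are defined as the last assessment available before or on the start date of study treatment". The same section defines the start date as the first date with a nonzero dose, without a clock time. The ECG section of each SAP (2.8.4.1) sets no baseline of its own. It counts patients with a new QT/QTcF value above 450, 480 or 500 ms and patients with a rise above 30 or 60 ms. The core SAP adds an ECG shift table from baseline.

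**Protocol, baseline.** The glossary has "Value from the last assessment prior to first dosing". Section 7.1.1.3 says "the last value prior to the start of study drug will be considered the baseline value". For QTcF, section 7.2.2.6.2 requires Day 1 pre-dose ECGs in triplicate and adds: "The mean of the QTcF from these 3 tracings is used as the baseline QTcF". Section 7.2.2.7 repeats it: "The mean of the QTcF values from these three ECG tracings is used to determine the mean baseline QTcF".

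**Protocol, schedule.** Section 2.2.6: "Cardiac monitoring will include 12-lead Safety ECGs at pre-dose (Day 1) and 1.5 hours post-dose at each visit the patient receives study drug". Table 7-6 lists Day 1 twice, once pre-dose and once at "1.5 hours Post-dose".

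**Declared changes.** The introductions of both SAPs tie the plan to the protocol. Section 4 of each lists departures from it; baseline is not among them.

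**The concern.** A rule that takes the last record on a date picks the wrong record when two assessments of the same kind fall on that date, one on each side of the first dose. For ECG that is the scheduled situation in every patient. QT prolongation is an adverse event of special interest (protocol 8.1.3), and every notable-QTcF count depends on the baseline. Two things go wrong under the literal rule. The ECG timed near peak concentration after the first dose stops being a post-baseline observation. And a single tracing takes the place of a mean of three, which makes every later change from baseline noisier.

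**Working it through.** The plan gives no figure to reproduce here. The check applies both rules to the scheduled ECGs and then sizes the difference.

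**1. Which record each rule selects.** On Day 1 the order is three pre-dose tracings, then one at 1.5 h.
- SAP rule (latest record dated on or before the start date): the 1.5 h tracing.
- Protocol rule: the mean of the three pre-dose tracings.
- SAP rule with only a pre-dose condition added: the third pre-dose tracing, still not the mean.

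**2. Individual patients (illustrative values, ms).** Neither meets a protocol QT trigger.

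| Pre-dose mean | Day 1, 1.5 h | Week 12 | Protocol baseline | Literal SAP baseline |
|---|---|---|---|---|
| 430 | 455 | 470 | 470 − 430 = +40; flags >30 and >450 | 470 − 455 = +15; no flag (baseline already above 450) |
| 430 | 415 | 448 | 448 − 430 = +18; no flag | 448 − 415 = +33; flag >30 |

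**3. Mean shift after the first dose.** Protocol 1.2.1.2.4 predicts 4.1 ms at 174 ng/mL (20 mg) and 6.3 ms at 284 ng/mL (30 mg). The slope is (6.3 − 4.1)/(284 − 174) = 0.02 ms per ng/mL and the intercept is 4.1 − 0.02 × 174 = 0.62 ms. The first dose is 2 mg. Scaling Cmax down tenfold in dose, with an assumed 2.0- to 2.4-fold change per doubling, gives 174/2.0^3.32 = 17.4 to 174/2.4^3.32 = 9.5 ng/mL. The drug effect is then about 0.2–0.35 ms, or 0.8–1.0 ms with the intercept. In the placebo arm the Day 1 post-dose ECG is drug-free.

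**4. Noise at one later ECG, no true change.** With within-patient SD σ and independent tracings, the change has variance 2σ² for a single-tracing baseline and (4/3)σ² for a triplicate mean. The chance of exceeding 30 ms is 1 − Φ(30/SD of change). For σ = 8, 10, 12 ms this is 0.4, 1.7, 3.9% (single) against 0.06, 0.5, 1.5% (mean of three).

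**5. Noise over the scheduled ECGs (simulation).** Assumptions: constant true QTcF, full attendance, a between-day share of variance of 0 or 0.5 (the two ends of each range), and removal of patients with a Day 1 rise above 30 ms. The SDs and the variance split are not in the documents. The osilodrostat arm has 15 ECGs from Week 2 to Week 48. The placebo arm has 11 from Week 14, because both SAPs exclude its placebo-controlled data from the overall period.

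| SD | Any >30 flag, 15 ECGs: protocol / literal | Lost + gained, 15 ECGs (share 0; 0.5) | Status changed: 15 ECGs / 11 ECGs | Patients: 46 × p15 + 23 × p11 |
|---|---|---|---|---|
| 8 | 0.8–2.3% / 4.0% | 0.6+3.8; 1.1+2.9% | 4.0–4.4% / 3.2–3.5% | 2.6–2.8 |
| 10 | 5.9–10.1% / 13.4% | 3.7+11.3; 4.2+7.5% | 11.7–15.0% / 9.9–12.3% | 7.7–9.7 |
| 12 | 16.2–21.6% / 25.0–25.4% | 8.6+17.8; 7.6+10.9% | 18.5–26.4% / 16.4–22.8% | 12.3–17.4 |

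For the randomized comparison in Period 1 (4 ECGs), 1.4–1.5%, 5.1–6.0% and 9.5–12.4% change status. Times 69, that is about 1, 4 and 7–9 patients. Gains exceed losses in every setting.

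**6. A smaller related point, final SAP 2.8.1.2.** The denominator for adverse events of special interest by onset is everyone still on study when the interval starts. Sections 2.1.1 and 2.8 exclude placebo-arm Period 1 data, and 2.8 names an overall group. If intervals run from randomized baseline, the overall figure for Baseline to Week 12 divides by 69 instead of 46 planned patients. The factor is 46/69 = 0.667, so 20% would print as 13%. The osilodrostat-arm column is unaffected.

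**The case against.** The strongest reply is that the documents, read together, already settle the matter. The protocol is explicit, both SAPs say they rest on it, and neither declares a change. The literal rule also clashes with the SAPs' own periods: in section 2.8 the on-treatment period starts on the day of first dose, so one ECG would be both baseline and on-treatment. ECG date and time are recorded, so a programmer can pick the pre-dose tracings. All of this stands as evidence that the literal reading is unintended. It does not remove the defect. The SAP sentence expressly governs efficacy and safety evaluations, gives a different rule, and no text tells the programmer to set it aside.

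It is also fair that the drug effect at 2 mg is under about 1 ms, and that the patient counts in the working come from assumed SDs whose results span roughly sixfold. The conflict of text does not depend on them.

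A reader might infer that the rule hides QT signals. The calculations point the other way on balance: more >30 ms flags appear than disappear, although individual true flags can be lost. Nor is a large Day 1 rise lost from the study. The protocol acts on "an increase in QTcF > 30 msec from the mean baseline value, or the QTcF is > 480 msec", with a repeat triplicate and cardiologist review, and a Day 1 rise above 30 ms is recorded as an adverse event (7.2.2.6.2).

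A reader might also infer firm limits, for example that no true rise above 60 ms could escape the >30 ms row because continuing patients rose by at most 30 ms on Day 1. The documents do not support strict limits, since discontinuation depends on the triplicate mean and the cardiologist's review and not on the single tracing.

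**Conclusion.** The baseline sentence is wrong as written for ECG in both SAPs and should be corrected. It is probably a wording error and not a decision to depart from the protocol; nothing in the documents shows that the post-dose ECG was meant to be used.

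The reach is narrow: notable QT/QTcF counts in both SAPs and the ECG shift table in the core SAP. Extending it further is not supported. Protocol 7.1.1.3 has the other Day 1 assessments taken before drug, so laboratory and vital-sign baselines hold. Baseline urinary free cortisol is collected before treatment starts, and the primary and key secondary endpoints use no baseline value. The on-site QT rules work from the protocol's own triplicate mean.

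The size is about 3, 8–10 and 12–17 of 69 planned patients changing >30 ms status in the overall osilodrostat period of the core phase, and about 1, 4 and 7–9 in Period 1. This rests on assumed SDs of 8, 10 and 12 ms, no drug effect, full attendance and the planned 46 + 23 patients.

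The onset-interval denominator in the final SAP is a minor alignment. The exposure formula in final SAP 2.4.1.1 starts at first study treatment, which could suggest that placebo time is counted. The text beside it excludes placebo exposure, so this is an editorial mismatch only.

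**What to change.** In section 2.1.1 of both SAPs:
- Define baseline as the last assessment before the first dose of study treatment, by date and time.
- State that the QTcF baseline is the mean of the Day 1 pre-dose triplicate and that the Day 1 1.5 h ECG is post-baseline. Both sentences are needed, because a pre-dose condition alone still selects one tracing.

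In the final SAP only:
- Section 2.8.1.2: count only osilodrostat-exposed patients in the denominator of each onset interval.
- Section 2.4.1.1: start the exposure formula at the first osilodrostat dose, to match its text.

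The cost is two sentences per SAP and two wording edits. The triplicate and the ECG date and time are already collected, so no new data are needed. If any ECG table was programmed from the literal sentence, it has to be rerun.

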2.2 Analysis sets

2.2.1 Full Analysis Set

The Full Analysis Set (FAS) comprises all randomized patients who have received at least one dose of study drug (osilodrostat or placebo). According to the intent-to-treat (ITT) principle, patients will be analyzed according to the treatment and stratum they have been assigned to during the randomization. This is the default analysis set for efficacy. The randomization is stratified by history of pituitary irradiation yes/no.

